5.4 Duration of Therapy

If at any time the constraints of this protocol are considered to be detrimental to the patient's health and/or the patient no longer wishes to continue protocol therapy, the protocol therapy should be discontinued and the reason(s) for discontinuation documented in the case report forms.

In the absence of treatment delays due to adverse events, treatment may continue indefinitely until one of the following criteria applies:

- Documented and confirmed disease progression
- Death
- Adverse event(s) that, in the judgment of the investigator, may cause severe or permanent harm or which rule out continuation of study drug
- General or specific changes in the patient's condition render the patient unacceptable for further treatment in the judgment of the investigator
- Suspected pregnancy
- Serious non-compliance with the study protocol
- Lost to follow-up
- Patient withdraws consent
- Investigator removes the patient from study
- The Siteman Cancer Center decides to close the study

Patients who prematurely discontinue treatment for any reason other than withdrawal of consent will be followed as indicated in the study calendar.

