6.0 DOSE DELAYS/DOSE MODIFICATIONS

As a general rule, if dose reduction of pazopanib is necessary, the dose should be reduced stepwise by 200 mg at each step, and the subject should be monitored for approximately 10 to 14 days at each dose level. If toxicity does not abate during this monitoring time, the pazopanib may need to be interrupted and/or the dose further decreased with continued monitoring for an additional 10-14 days at each dose level, and so on.

If the toxicity has abated with reduction of the dose and dose re-escalation is considered safe by the investigator, the pazopanib dose can then be increased step-wise back to the pre-event dose

(in 200 mg increments, after monitoring for 10-14 days at each dose level to ensure that toxicity did not recur or worsen).

Dose-level	0	-1	-2	-3	-4
Dose	800 mg QD	600 mg QD	400 mg QD	200 mg QD	Discontinue

For patients at dose-level -3, 200 mg QD, a maximum dose delay of 14 days is allowed for management of toxicities. If toxicity does not resolve in 14 days, the patient should be discontinued from study.

Dose Modification Algorithms for Potential Treatment-Related Adverse Events

AE Terms & Descriptions	Dose Modification Algorithms
Hypertension	
(A). Asymptomatic and persistent SBP of ≥ 140 - <170 mmHg, or DBP ≥ 90 - <110 mmHg, or a clinically significant increase in DBP of 20 mmHg (but still below 110 mmHg).	Step 1. Continue pazopanib at the current dose. Step 2. Adjust current or initiate new antihypertensive medication(s). Step 3. Titrate antihypertensive medication(s) during next 2 weeks as indicated to achieve well-controlled ^a blood pressure (BP). If BP is not well-controlled within 2 weeks, consider referral to a specialist and go to scenario (B).
(B). Asymptomatic SBP ≥ 170 mmHg, or DBP ≥ 110 mmHg, or failure to achieve well-controlled BP within 2 weeks in scenario (A).	Step 1. Consider reducing or interrupting pazopanib, as clinically indicated. Step 2. Adjust current or initiate new antihypertensive medication. Step 3. Titrate antihypertensive medication(s) during next 2 weeks as indicated to achieve well-controlled BP. Step 4. Once BP is well-controlled, restart pazopanib dose-reduced by 200 mg if it was interrupted.

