(C). Symptomatic hypertension or recurring SBP ≥ 170 mmHg, or DBP ≥ 110 mmHg, despite modification of antihypertensive medication(s)	Step 1. Interrupt pazopanib. Step 2. Adjust current or initiate new antihypertensive medication(s). Step 3. Titrate antihypertensive medication(s) during next 2 weeks as indicated to achieve well-controlled BP. Referral to a specialist for further evaluation and follow-up is also recommended. Step 4. Once BP is well-controlled, restart pazopanib dose-reduced by 200 mg.
(D). Refractory hypertension unresponsive to above interventions.	Discontinue pazopanib and continue follow-up per protocol.
Proteinuria	
UPC <3	Continue pazopanib at the current dose; monitor as clinically indicated
UPC ≥ 3 or 24-h urine protein ≥ 3 g	Step 1. Interrupt pazopanib. Step 2. Weekly UPC or 24-hr urine protein monitoring until UPC is <3 or 24-hr urine protein is <3 g. Then restart pazopanib dose-reduced by 200 mg. Step 3. If UPC ≥ 3 or 24-h urine protein ≥ 3 g recurs, repeat steps 1 and 2 Step 4. If UPC ≥ 3 or 24-hr urine protein ≥ 3 g recurs and the pazopanib dose can no longer be reduced, discontinue pazopanib and continue follow-up per protocol.

AE Terms & Descriptions	Dose Modification Algorithms
Hemorrhage/Bleeding: Investigate and document underlying etiology of the bleeding	
Grade 1	For hemoptysis, interrupt pazopanib and consider whether further treatment with pazopanib is appropriate. For other grade 1 hemorrhage/bleeding event, continue pazopanib at the current dose; monitor as clinically indicated.
Grade 2	Step 1. If pulmonary or GI bleed (other than hemorrhoidal bleeding), discontinue pazopanib and continue follow-up per protocol. Otherwise, interrupt pazopanib until the AE resolved to \leq grade 1. Step 2. Restart pazopanib; consider reducing dose and monitor as clinically indicated.
Grade 3 or 4, or recurrent \geq grade 2 event after dose interruption/reduction.	Discontinue pazopanib and continue with follow-up per protocol.
Venous Thrombosis (DVT, PE)	
Grade 2	Continue pazopanib at the current dose; monitor as clinically indicated

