Grade 3	Step 1. Interrupt pazopanib. Step 2. Initiate and monitor anticoagulation as clinically indicated. Step 3. Resume pazopanib at reduced dose only if all of the following criteria are met: 
 • The subject must have been treated with anticoagulant at the desired level of anticoagulation for at least one week. • No grade 3 or 4 or clinically significant grade 2 hemorrhagic events have occurred while on anticoagulation treatment. Subject should be monitored as clinically indicated during anticoagulation treatment and after resuming study treatment. When treating with warfarin, international normalized ratio (INR) should be monitored within three to five days after any change in pazopanib dosing (e.g., re initiating, escalating/de-escalating, or discontinuing pazopanib), and then at least weekly until the INR is stable. The dose of warfarin (or its derivatives) may need to be adjusted to maintain the desired level of anticoagulation
Grade 4 and/or PE	Discontinue pazopanib and continue follow-up per protocol.
Arterial Thrombosis/Ischemia	
Any grade	Discontinue pazopanib and continue follow-up per protocol.
Thrombocytopenia: Investigate and document underlying cause	
Grade 1 or 2	Continue pazopanib with current dose; monitor as clinically indicated.
Grade 3 or 4	Step 1. Interrupt pazopanib until toxicity resolves to \leq grade 2. Step 2. Restart pazopanib dose-reduced by 200 mg and monitor as clinically indicated. If no recovery to \leq grade 2 or recurrent grade 3 or 4 thrombocytopenia, discontinue pazopanib and follow-up per protocol
Anemia: No specific dose reduction rules are indicated for anemia unless due to hemorrhage or bleeding as noted above.	
Palmar-plantar Erythrodysesthesia Syndrome	
Grade 1 Minimal skin changes or dermatitis without pain (erythema, edema,	Continue pazopanib with current dose.

AE Terms & Descriptions	Dose Modification Algorithms
hyperkeratosis)	
Grade 2 Skin changes with pain; limiting instrumental activities of daily living (peeling, blisters, edema, bleed, hyperkeratosis)	Step 1. Hold pazopanib. Step 2. Treat as clinically appropriate. Step 3. Upon resolution to grade 1 or better, restart pazopanib with a dose reduction to 400 mg. Step 4. If recurrent, consider a further dose reduction to 200 mg or discontinuation.
Grade 3 Severe skin changes with pain and limiting self-care activities of daily living	Discontinue pazopanib
Other Clinically Significant Adverse Events^b	

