Grade 1	Continue pazopanib; monitor as clinically indicated.
Grade 2 or 3, if clinically significant	Step 1. Interrupt pazopanib until toxicity resolves to \leq Grade 1. Step 2. Restart pazopanib dose-reduced by 200 mg and monitor as clinically indicated.
Grade 4	Discontinue pazopanib and continue follow-up per protocol.
Prolongation of QTc Interval: If the QTc is prolonged, the ECG should be manually read to ensure accuracy of the reading. The values below refer to manually-read ECGs.	
QTc \geq 480-500 msec	Continue pazopanib; monitor as clinically indicated.
QTc \geq 500 msec	Discontinue pazopanib and continue follow-up per protocol.

a. Well-controlled BP defined as SBP <140 mmHg and mean DBP <90 mmHg.

b. AEs are graded according to NCI Common Terminology Criteria for Adverse Events v4.0 (NCI CTCAE v4)

Guidelines for Management of Treatment Emergent Hepatotoxicity

Event	Dose Modification Algorithms
(A). ALT of \leq 3.0 x ULN	Continue pazopanib at current dose with full panel LFTs ^a monitored as per protocol.
(B). ALT >3.0 x ULN to \leq 8.0 x ULN without bilirubin elevation (defined as total bilirubin ^b <2.0 x ULN or direct bilirubin \leq 35%) and without hypersensitivity symptoms (e.g., fever, rash)	Step 1. Continue pazopanib at current dose levels. Step 2. Monitor subject closely for clinical signs and symptoms; perform full panel LFTs ^a weekly or more frequently if clinically indicated until ALT is reduced to grade 1.
(C). ALT >8.0 x ULN without bilirubin elevation (defined as total bilirubin ^b <2.0 x ULN or direct bilirubin \leq 35%) and without hypersensitivity symptoms (e.g., fever, rash)	1st occurrence – Liver Event Interruption Criteria: Step 1. Interrupt pazopanib until toxicity resolves to \leq grade 1 or baseline. Report the event to Novartis as an SAE within 24 hours of learning of its occurrence. Make every reasonable attempt to have subjects return to the clinic within 24 to 72 hours for repeat liver chemistries and liver event follow up assessments. Step 2. Liver imaging and other laboratory investigations should be considered as clinically appropriate. Step 3. Monitor subject closely for clinical signs and symptoms; perform full panel LFTs ^a weekly or more frequently if clinically indicated until ALT is reduced to grade 1. Step 4. If the subject is benefiting from the study treatment, re-treatment may be considered if ALL following criteria are met: - ALT reduced to Grade 1

Event	Dose Modification Algorithms

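### The grade 2 palmar-plantar row restarts pazopanib at a fixed 400 mg, which read literally is no reduction for a patient already at 400 mg and gives no usable dose for one at 200 mg

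*Combined protocol and SAP*

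**What the plan says.** Section 6.0 sets a dose ladder of 800, 600, 400 and 200 mg daily, with level -4 meaning discontinuation. Its general rule is that "if dose reduction of pazopanib is necessary, the dose should be reduced stepwise by 200 mg at each step".

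The grade 2 palmar-plantar row has four steps. Pazopanib is held, the reaction is treated, and then Step 3 applies: "Upon resolution to grade 1 or better, restart pazopanib with a dose reduction to 400 mg". Step 4 deals with a second event: "If recurrent, consider a further dose reduction to 200 mg or discontinuation". Grade 3 palmar-plantar reactions lead to discontinuation.

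Other rows define the cut relative to the current dose. Hypertension scenario C reads "Once BP is well-controlled, restart pazopanib dose-reduced by 200 mg", and the row for other clinically significant grade 2 or 3 events reads "Restart pazopanib dose-reduced by 200 mg and monitor as clinically indicated". The proteinuria row also cuts by 200 mg, repeats the cut on recurrence, and says what to do at the floor: if proteinuria recurs and "the pazopanib dose can no longer be reduced, discontinue pazopanib and continue follow-up per protocol".

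At 200 mg, Section 6.0 allows at most 14 days of delay for toxicity; if the toxicity has not resolved by then, the patient comes off study.

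**The concern.** Step 3 is written as if the patient is always above 400 mg when the skin reaction appears. The table's own rules allow a patient to be at 400 or 200 mg by then because of other toxicities. The only specific instruction in the row then either leaves the dose where it was or cannot be carried out as a reduction.

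What is at stake is participant safety. Grade 2 in this row means painful skin changes that limit instrumental daily activities. A patient at 400 mg managed by the letter of the row would resume the dose at which that reaction occurred, and a cut would be considered only after a recurrence.

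**Working it through.** There is no sample size, power or error rate to reproduce. The check applies Step 3 to each active dose level and compares the result with the general rule. All inputs come from Section 6.0: the ladder, the fixed 400 mg restart, and the 200 mg general step.

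**Can a patient be at 400 or 200 mg before a first palmar-plantar event?** Yes.
- Two relative cuts: 800 - 200 - 200 = 400 mg, for example one under hypertension C and one under the row for other events.
- Three relative cuts: 800 - 3 × 200 = 200 mg. The proteinuria row alone can do this, because its cut repeats.

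**What does each rule give?** Change under Step 3 = 400 - dose at onset. General rule = dose at onset - 200, with discontinuation at the floor.

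| Dose at onset | Step 3 restart | Change under Step 3 | General rule |
|---|---|---|---|
| 800 mg | 400 mg | -400 mg (two levels) | 600 mg |
| 600 mg | 400 mg | -200 mg (one level) | 400 mg |
| 400 mg | 400 mg | 0 mg (no reduction) | 200 mg |
| 200 mg | not possible as a reduction | +200 mg if only the number is read | discontinue |

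Step 3 produces a reduction at two of the four levels. It agrees with the general rule only at 600 mg.

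**Does other text settle the two failing cases?**
- *General rule and ladder.* They would give 400 to 200 mg, and 200 mg to discontinuation. But the text calls itself a general rule, and the palmar-plantar row already departs from it at 800 mg by cutting two levels. No sentence says which prevails.
- *Step 4.* It applies only to recurrence, so it does not govern a first event.
- *The 14-day limit at 200 mg.* It covers toxicity that fails to resolve. It gives no restart dose when toxicity does resolve, which is the situation Step 3 addresses.
- *Further-decrease clause.* Section 6.0 adds "If toxicity does not abate during this monitoring time, the pazopanib may need to be interrupted and/or the dose further decreased". This permits more action if toxicity persists, but Step 3 starts from toxicity that has settled.
- *Section 5.4.* Therapy stops "If at any time the constraints of this protocol are considered to be detrimental" to the patient's health. This is a general escape that depends on judgement. It does not supply a restart dose.

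**The case against.** The strongest reply is that Step 3 speaks of a reduction, so it presupposes a dose above 400 mg. On that view the row is silent at 400 and 200 mg, and the general rule and ladder fill the silence: a row that departs from a default where it speaks does not displace the default where it is silent. Most other rows also leave the floor to the ladder; only proteinuria spells it out.

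Much of this stands. The fallback is plausible, and many investigators would probably use it. But the row names a dose without a condition, and the documents do not say that the general rule governs when a specific row does not fit. The other rows that specify a 200 mg cut at least start from the current dose, so they yield a workable dose at 400 mg; this one does not.

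The protections also stand. Drug is held until the reaction is grade 1 or better, so nobody is dosed through the painful phase. Grade 3 ends treatment, and delay at 200 mg is capped.

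A reader might infer that the protocol directs a doubling of dose from 200 to 400 mg. The documents do not support that. The step is worded as a reduction, and Section 6.0 allows re-escalation only back to the pre-event dose. The fair reading is that the row gives no usable restart dose at 200 mg.

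**Conclusion.** The point holds as a minor fault in a dosing rule. Read literally, Step 3 gives a 0 mg cut for onset at 400 mg, and it supplies no workable restart dose for onset at 200 mg. The outcomes for onset at 800 and 600 mg are not in question. The conclusion rests on the wording of Section 6.0 and on no assumed rates.

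Two further inferences should not be drawn. First, a reader might want an expected number of affected patients. The documents give neither the rate of palmar-plantar events nor the share of patients reduced for other toxicities, so any figure would only restate its assumptions. What can be said is that the trial plans 20 patients, all starting at 800 mg, and that a patient must have had at least two earlier cuts and not been re-escalated. The case should therefore be uncommon, but that is a judgement and not an estimate. Second, a reader might suspect an effect on the efficacy results. The row has no part in how response or PFS is defined (Sections 12.4 and 12.4.5) or in the descriptive analysis (Section 14.2).

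**What to change.** Reword Step 3 of the grade 2 palmar-plantar row along these lines: once the reaction has settled to grade 1 or less, resume at 400 mg or at one dose level (200 mg) below the dose at onset, whichever is lower, and never above the dose at onset. For onset at 200 mg, go to level -4 (discontinue) unless the investigator documents that the patient is benefiting and that resuming 200 mg is safe.

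The restart dose is then min(400, dose at onset - 200):
- 800 mg: min(400, 600) = 400 mg, unchanged
- 600 mg: min(400, 400) = 400 mg, unchanged
- 400 mg: min(400, 200) = 200 mg
- 200 mg: min(400, 0) = 0, that is level -4, subject to the documented exception

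The exception is there because Step 4 asks the investigator only to consider 200 mg or stopping, even after a recurrence. Compulsory discontinuation after a first, resolved event would be stricter than the row's own approach.

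The cost is a wording change to one step of one row, with no added visits, tests or patients. It can wait for the next amendment. The downside is that an occasional patient at 400 mg will receive 200 mg after a first event, where the literal text would have kept 400 mg.

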	
 - Total bilirubin <1.5 x ULN or direct bilirubin ≤35% - No hypersensitivity signs or symptoms - Subject is benefiting from therapy. 
Recurrence – Liver Event Stopping Criteria: Discontinue pazopanib permanently and monitor subject closely for clinical signs and symptoms; perform full panel LFTs^a weekly or more frequently if clinically indicated until ALT is reduced to grade 1.

(D). ALT >3.0 x ULN with concomitant elevation in bilirubin^b (defined as total bilirubin ≥2.0 x ULN; with direct bilirubin >35%) or with hypersensitivity symptoms (e.g., fever, rash).
	
Liver Event Stopping Criteria: Step 1. Discontinue pazopanib immediately, report the event to Novartis as an SAE within 24 hours of learning of its occurrence. Make every reasonable attempt to have subjects return to the clinic within 24 hours for repeat liver chemistries and liver event follow up assessments. Step 2. Consult a gastroenterologist / hepatologist and perform the following assessments to identify potential co-factors:
 
 - Eosinophil count - Viral serology for hepatitis A, B, C and E, cytomegalovirus, Epstein-Barr virus (IgM antibody, heterophile antibody, or monospot testing) - Anti-nuclear antibody, anti-smooth muscle antibody, Type 1 anti-liver kidney microsomal antibodies. - Serum creatinine phosphokinase for possible muscle injury caused LFT elevation - Liver imaging - Consider toxicological blood screen for possible contributing chemical/medical entities 
Step 3. Monitor subject closely for clinical signs and symptoms; record the appearance or worsening of clinical symptoms of hepatitis, or hypersensitivity, such as fatigue, nausea, vomiting, right upper quadrant pain or tenderness, fever rash or eosinophilia as relevant on the AE report form. Perform full panel LFTs^a weekly or more frequently if clinically indicated until LFTs are reduced to grade 1.

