10.0 STUDY CALENDAR

Screening/baseline evaluations are to be conducted no more than 14 days prior to start of protocol therapy. Scans and x-rays must be done no more than 4 weeks prior to the start of the protocol therapy. All visits have a window of +/- 3 days.

	Screening	D1 of each cycle	C1D8	C1D15 and C2D15	End of every even-numbered cycle	EOT	F/U ⁹
Informed consent	X						
PE, H&P, PS	X	X				X	
VS	X	X ¹	X			X	
CBC	X	X	X			X	
CMP	X	X	X			X	
LFTs ²	X	X ²	X ²	X ²		X	
Pregnancy test ³	X					X	
UPC	X	X ¹⁰				X	
TSH, T4	X	X ⁴					
PT/PTT, INR	X					X	
ECG	X	X ⁵					
CT scan	X				X	X	
Pazopanib		X ----- X ⁶					
Collect/review medication diary		X					
Toxicity assessment	X	X				X ¹¹	
Tissue for Research Purposes	X ⁷					X ⁷	

1. **Monitoring of BP only at Day 7 +/- 3 days.** Can be assessed by any method as long as the study physician is informed of the measurement, verifies any measurement that is not normal, and takes appropriate action.

2. Monitor serum liver tests before initiation of treatment with pazopanib and C1D15, C2D1, C2D15, C3D1, C4D1, C5D1, and as clinically indicated. Periodic monitoring should continue after C5.

3. Women of childbearing potential only.

4. Monitor between every 8 to every 16 weeks.

5. C2D1, C4D1, C7D1 and then every 16 weeks (Day 1 of every fourth cycle) until EOT.

6. To be taken PO QD. Each cycle is 4 weeks long.

7. Optional tissue for research purposes per section 9.1.9. Patients will be followed every 2 months for recurrence and survival until death.

10. Day 1 of each cycle through Cycle 6, then Day 1 of every even-numbered cycle thereafter.

11. Last assessment to take place 30 days following end of treatment.

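### After ALT above 8 x ULN, required weekly liver tests end at the same ALT value that permits re-treatment, and no liver test is dated from the restart

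*Combined protocol and SAP*

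**What the plan says.** Section 6.0, row (C) of the hepatotoxicity guidelines, covers ALT above 8 x ULN without bilirubin elevation or hypersensitivity symptoms. At the first occurrence pazopanib is interrupted, and every reasonable attempt is made to have the patient "return to the clinic within 24 to 72 hours for repeat liver chemistries and liver event follow up assessments". Step 3 sets full panel LFTs weekly or more often, and the text runs straight on into Step 4: "if clinically indicated until ALT is reduced to grade 1. Step 4. If the subject is benefiting from the study treatment, re-treatment may be considered". The Step 4 criteria are ALT at grade 1, a bilirubin limit, no hypersensitivity, and benefit from therapy. None of them lowers the dose or sets a test after the restart. The rule for a recurrence is "Discontinue pazopanib permanently and monitor subject closely for clinical signs and symptoms", with weekly LFTs from that point.

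Row (A) covers ALT up to 3 x ULN and refers to LFTs as scheduled in the protocol. The section 10.0 grid marks LFTs on Day 1 of each cycle and at C1D8, C1D15 and C2D15. After the pre-treatment test, footnote 2 lists "C1D15, C2D1, C2D15, C3D1, C4D1, C5D1, and as clinically indicated. Periodic monitoring should continue after C5". The calendar also states: "All visits have a window of +/- 3 days".

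Two general rules in section 6.0 bear on this. After a dose reduction, "the subject should be monitored for approximately 10 to 14 days at each dose level". Re-escalation proceeds stepwise "after monitoring for 10-14 days at each dose level to ensure that toxicity did not recur or worsen".

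**The concern.** Grade 1 in Step 4 is reached off drug. It shows that the liver has recovered, not that renewed dosing is tolerated. Yet it is the point at which the required weekly testing stops.

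The next row up makes the contrast clear. A row (B) patient (ALT above 3 and up to 8 x ULN) stays on drug and is tested weekly until ALT is grade 1. A row (C) patient, whose ALT was higher, may go back on drug at an unreduced dose. No weekly test is required unless some later test exceeds 3 x ULN and brings row (B) into play.

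What is at stake is patient safety. A recurrence ends treatment permanently, but that rule can act only once the recurrence has been measured. Watching for signs and symptoms would not find a symptomless ALT rise.

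**Working it through.** The plan states no figure for this interval, so there is none to reproduce. The check counts days from a restart to the next required LFT.

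**Inputs.** Cycles are 28 days (section 5.1), so day = 28 x (cycle - 1) + day of cycle. The section 10.0 grid then gives LFT days 8, 15, 29, 43, 57, 85, 113 and every 28 days after that. Footnote 2 alone gives 15, 29, 43, 57, 85 and 113, and then no dates. Row (A) is taken to apply at ALT grade 1. The documents do not print the grade limits, but row (B) tests from above 3 x ULN down to grade 1, which fits.

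**Formula.** Wait = next LFT day - restart day, with cycle numbering continuing through the hold.

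| Restart | Study days | Wait, grid | Wait, footnote 2 alone |
|---|---|---|---|
| After C1D15 is due, before C3D1 | 15-42 | 1-14 days | 1-14 days |
| C2D15 to before C3D1 | 43-56 | 57 - 43 = 14, down to 1 | same |
| C3D1 to C4D28 | 57-112 | 85 - 57 = 28, down to 1 | same |
| C5D1 or later | from 113 | 1-28 days | no dated test |

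Restarts before day 15 also wait less than 14 days. The full 28 days needs a restart on Day 1 of a cycle. A C3D1 restart then takes 28 daily doses (days 57 to 84) before the day 85 test.

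**Visit window.** It lengthens both limits. If the next visit is 3 days late, 14 becomes 17 (day 43 to 60) and 28 becomes 31 (day 57 to 88). If the preceding visit and the restart are also 3 days early, they become 20 (day 40 to 60) and 34 (day 54 to 88).

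**Illustration.** Take an event found at C3D1 (day 57), with the restart on a weekly test day. Holds of 1, 2, 3 and 4 weeks give restarts on days 64, 71, 78 and 85, and waits of 21, 14, 7 and 28 days. If the 24 to 72 hour recheck sets the weekly series, the waits become 18-20, 11-13, 4-6 and 25-27 days. The date of the restart decides, not the date of the event: an event at C2D15 (day 43) with a 2-week hold restarts on day 57 and waits 28 days.

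**Comparison.** On the grid, a new starter has three LFTs in the first 28 days (days 8, 15 and 29). A patient re-treated at C3D1 or later has one.

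**Other numbering rules.** If numbering is frozen during the hold, the wait is about 7 days for an event at C1D8. It is 14 days for one at C1D15, C2D1 or C2D15, and 28 for one on a Day 1 test from C3D1 on. If the calendar were restarted at C1D1 the gap would disappear, but no text says so.

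**The case against.** The strongest reply is that testing after a restart is covered, by the calendar plus clinical discretion. Re-treatment is optional, row (A) names the schedule, and footnote 2 allows earlier tests when indicated. That is a fair reading of the intent. What remains is that an earlier test is permitted, not required.

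Second, the general rule of 10 to 14 days at each dose level would cover a restart at a lower dose, and sensible monitoring after an ALT event means an LFT. This has force, although the rule names no LFT. It does not reach a full-dose restart, which row (C) allows.

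Third, a reader might infer that row (C) stands out from the rest of section 6.0. The documents do not support that. The thrombocytopenia row also stops treatment on recurrence and leaves testing after the restart to clinical discretion. Proteinuria is monitored weekly "until UPC is <3 or 24-hr urine protein is <3 g. Then restart pazopanib dose-reduced by 200 mg", again with no test dated from the restart. Both rows, however, require a 200 mg reduction at restart, and row (C) does not. The rule that INR be checked within three to five days of a pazopanib dosing change concerns warfarin and is no like-for-like comparator. It shows only that the protocol can date a test from a restart.

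Fourth, a Day 1 restart, the worst case, falls on a scheduled LFT day, so a same-day value exists. That is true, but it describes the patient off drug.

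**Conclusion.** The point holds as a cheap improvement for patient safety. Following the plan as written, a patient re-exposed after ALT above 8 x ULN can take up to 28 daily doses, nominally, before a required LFT. That upper limit assumes continued cycle numbering and Day 1 tests in every cycle, which is the reading kinder to the plan. On footnote 2 alone, a restart at C5D1 or later has no dated test.

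A reader might infer that re-treated patients in general go four weeks untested, or that a typical delay can be quoted. Neither follows. The nominal wait is at most 14 days before C3D1 and 1 to 28 days afterwards. Nothing in the documents says how restart days or hold lengths are distributed, so an average would rest on invented weights. Nor do the documents support reading this as a threat to the trial's results. The response rate and PFS definitions, and N = 20, are untouched. No incidence of ALT above 8 x ULN is given, and with 20 patients few would be affected.

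**What to change.** Add one sentence to row (C) Step 4 and repeat it in calendar footnote 2: *From the day of re-treatment, perform full panel LFTs weekly for at least 4 weeks (the safety lead may extend this to 8), then return to the study calendar.* Weekly is row (C)'s own interval carried forward. The first required test then comes 7 days after the restart, however cycles are numbered. The 4-week minimum is a proposal, because the documents give no basis for a particular duration.

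Cost per re-treated patient, for a restart at C1D15 or later on the grid reading:

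- 4 weeks: 4 weekly tests less the 1-2 already scheduled = 2-3 extra draws.
- 8 weeks: 8 weekly tests less the 2-3 already scheduled = 5-6 extra draws.

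This lets a weekly draw also serve as the calendar test. On footnote 2 alone, a restart at C5D1 or later has no scheduled tests to subtract, so the extra draws would be 4 or 8. The extra visits are the only other burden, and the sample size and analyses do not change.
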